8 DEFINITIONS AND DERIVED VARIABLES

8.1 Demography and Baseline Characteristics

Age: Age will be calculated using the Date of Birth and the date of the randomization, and present as age at last birthday as an integer.

$$\text{Age} = \text{Integer part of } [(Date \text{ of Baseline visit} - Date \text{ of Birth}) / 365.25]$$

Body Mass Index (BMI): BMI is the subject's body weight in kilograms divided by the square of the subject's height in meters.

$$\text{BMI} = \text{Weight in kilograms} / (\text{Height in meters})^2$$

Predicted Body Weight (PBW): The dose of hMSC product will be given based on patient's predicted body weight. PBW will be calculated by gender and height using the following reference formulas:

$$\text{Male: PBW (kg)} = 50 + 2.3 (\text{height (in)} - 60)$$

Female: PBW (kg) = 45.5 + 2.3 (height (in) – 60)

8.2 Acute Physiology, Age, Chronic Health Evaluation (APACHE) III

APACHE III is a validated scoring system to provide risk estimates for hospital mortality for individual ICU patients.(18) It is comprised of the sum of three components: an acute physiology score, an age score, and a chronic health problem score. Scores range from 0 to 299 (physiology, 0 to 252; chronic health evaluation, 0 to 23; age, 0 to 24, with higher values representing a worse prognosis. The worst values within 24 hours prior to randomization will be calculated for APACHE III score.

8.3 Sequential Organ Failure Assessment (SOFA) Score

SOFA score is a validated scoring system to describe a sequence of complications in the critically ill patients.(17) It is comprised of the sum of six organ system components and scores range from 0 to 24 (each component ranges from 0 to 4), with higher values representing a worse organ dysfunction and morbidity.

In this Phase 2b trial, we will calculate SOFA score on study day 0, 3, and 7. The worst values within 24 hours prior to randomization will be used for SOFA calculation on day 0, and the worst values on the calendar dates (midnight to midnight) will be used for follow-up days, according to the Brussels Organ Failure Table. We will calculate a modified non-pulmonary SOFA score, which comprises five of the six components as listed as below, the PaO₂/FiO₂ ratio for respiratory system will not be included:

- Neurological: Glasgow coma scale
- Cardiovascular: Mean arterial pressure or administration of vasopressors required
- Hepatic: Bilirubin
- Coagulation: Platelets
- Renal: Creatinine or urine output

During the ICU stay, if any of the component values are not obtained, their last non-missing values will be carried forward for score calculation. On the day of ICU discharge alive or after ICU discharge, the organ function will be treated as normal and non-pulmonary SOFA score will be zero.

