9.10 Day 7 Measurements

Arterial blood gases will be obtained anytime on days 7 if patient still has arterial line. If not obtained within the past 24 hours as part of clinical care, patients will have platelets, serum creatinine, total bilirubin and alanine aminotransferase (ALT) measured on day 7 (+/- 1 day) after administration of the study product if they are still hospitalized.

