6.1.4 Assessment after Enrollment: Reference Measurements

The following data will provide the basis for assessing protocol compliance and safety as well as between-group differences in several efficacy variables. Data for each of the variables will be recorded on the days shown in the Time-Events Schedule (**Table 2**) or until death, discharge from the ICU, or unassisted ventilation for 48 hours.

The following parameters will be measured and recorded at the time of Randomization as well as on subsequent dates using values closest in time to 8:00 A.M. on the days specified in the Time-Events Schedule (**Table 2**). The following conditions will be ensured prior to measurements: no endobronchial suctioning for 10 minutes; no invasive procedures or ventilator changes for 30 minutes. All vascular pressures will be zero-referenced to the mid-axillary line.

1. If receiving assisted ventilation, record daily up to day 7:
 - a. Tidal volume, FiO₂, PEEP, inspiratory plateau pressure, and mean airway pressures
 - b. Pressure during inspiration if on a pressure targeted mode (PSV, PCV, etc)
 - c. Arterial PaO₂, PaCO₂, pH and transcutaneous oxygen saturation
2. Fluid intake and output
3. Vital signs: Heart rate, systolic and diastolic blood pressure, body temperature, CVP
4. Modified Brussels Score data on days 0 through 14: Vasopressor use (Y/N), lowest systolic blood pressure, creatinine, bilirubin, and platelet count for the day
5. The date and value of the highest creatinine between days 15 and 28
6. Safety laboratory studies: all creatinine and bilirubin measurements will be recorded as above. Creatinine, bilirubin and ALT will be measured and recorded as safety labs on day 7 if not obtained as part of clinical care
7. Data regarding infections, including:
 - a. Surgical site and wound infections by CDC criteria
 - b. Ventilator associated or nosocomial pneumonia as diagnosed by CDC criteria
 - c. Culture-proven bacteremia
 - d. SARS-CoV-2 virus infection
8. Blood product transfusions
9. On-study procedures and surgical interventions
10. Co-enrollment in randomized clinical trials of other interventions and treatments related to SARS-CoV-2 infection
11. Inpatient medications (selected)
12. Must include all data needed for the 4-point acute lung injury score (including frontal chest radiograph), SOFA score, OSCI score and trauma registry index (if applicable)

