9 HANDLING OF MISSING VALUES AND OTHER DATA CONVENTIONS

Subjects will be allocated a 5-digit subject number and their inclusion/exclusion criteria eligibility will be determined prior to randomization. Subjects who do not satisfy all inclusion/exclusion criteria will be excluded from the study without randomization. Subjects who are not randomized are considered screening failures and a screening log will be required to record some de-identified data (see Clinical Protocol – Appendix C).

Prior to initiation of study product administration, subjects must achieve stable baseline for at least two hours and still be eligible for the trial, meeting the following key criteria and the timeline:

- Eligibility for the trial - ARDS develops less than 72 hours since first meeting ARDS criteria per the Berlin definition of ARDS
- Eligibility for the trial - Must begin to administer study product within 14 days of initial ICU admission
- Eligibility - The $\text{PaO}_2/\text{FiO}_2$ remains less than 250 mmHg after consent obtained and before study product is administered

For patients who have been randomized but who do not initiate study product administration, we will complete the following instruments: Screening Log, Infusion Eligibility Assessment and Pre-Infusion Baseline Assessment.

If a patient or surrogate withdraws consent for the study, we will discuss with the subject or surrogate the importance of complete data follow-up for the purposes of our safety analyses and determine if they are at least willing to participate in a follow up telephone call to ascertain survival. All patients who initiate study product administration will be analyzed for efficacy and safety endpoints, as well as incorporated with the relevant mixed model analyses, regardless of whether they complete or discontinue the study (e.g., consent withdrawn, infusion discontinuation, et al.).

We will make every effort to fulfill all the requirements of the protocol concerning the collection and management of data. Missing data will be summarized according to the number of subjects, the time-points where the data are missing and reasons of missing. No imputation will be applied

for missing data, unless indicated in the Statistical Analysis Plan and future amendments, if applicable.

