11 ANALYSIS SETS/POPULATIONS

A total of three populations will be used for all summaries and analyses. Subjects who have satisfied the population criteria will be classified in the designated population and will only be included in analyses for which they have available data.

Intent-to-Treat (ITT) Population

The analysis of the primary and secondary outcome will be based on the intention-to-treat (ITT) principle.

In this study, critical ill patients with ARDS often experience minute-to-minute changes in vital signs. Therefore, it is not uncommon that the patients will not achieve a stable baseline for 2 hours and initiate the infusion of study product within 14 days of initial ICU admission, or their $\text{PaO}_2:\text{FiO}_2$ ratio will improve to over 250 mmHg and they no longer qualify. In these cases, patients will be excluded and will not count toward the target enrollment of 120. Therefore, in this Phase 2b trial, the ITT population will be modified and include all subjects who are randomized, achieve baseline stability and initiate the study product administration, regardless of their compliance with the trial protocol or lack of study completion if allocated to the intervention group.

Since the study treatment is a single infusion of study product, a subject is unlikely to be withdrawn by investigators due to safety concerns because there is only a single treatment to be administered.

However, a surrogate or subject may withdraw consent for study participation either before, during or after study product administration. For subjects who are withdrawn prior to the initiation of study product infusion, they will not be included in ITT population. For subjects who are withdrawn during or after study product administration, they will be included in ITT population. The ITT population will be used to present primary efficacy endpoint and secondary efficacy endpoints by allocated randomization. Subjects will be summarized according to the treatment to which they were randomized, regardless of which treatment they actually received.

Per Protocol Population

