12.7.3 Sequential Organ Failure Assessment (SOFA) score

Non-pulmonary Sequential Organ Failure Assessment (SOFA) score will be calculated at baseline, 3, and 7 days, as described in **Section 8.3**.

The non-pulmonary SOFA scores at each timepoint, as well as the score changes from the baseline, will be summarized by allocated group, as mean and standard deviation.

Furthermore, non-pulmonary SOFA score, will be compared between treatment groups using a linear mix-effects regression model, which is similar to the analyses of the primary endpoint of oxygenation index.

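### SAP 8.3 gives no SOFA score to patients who die before day 3 or day 7, so the comparison leans modestly towards an arm with more early deaths, and its zero rule for ICU discharge overrides measured values

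*SAP*

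**What the plan says.** SAP 8.3 defines a "modified non-pulmonary SOFA score, which comprises five of the six components", each scored 0 to 4, on days 0, 3 and 7. Follow-up days take the worst values between midnight and midnight. Two rules fill gaps:

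- In ICU: "During the ICU stay, if any of the component values are not obtained, their last non-missing values will be carried forward for score calculation".
- Once out of ICU, starting with the day a patient leaves alive: "after ICU discharge, the organ function will be treated as normal and non-pulmonary SOFA score will be zero".

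Neither rule covers death. The rest of the SAP settles what happens by default:

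- SAP 6.1.4: reference data, which include the SOFA inputs, are recorded on the scheduled days "or until death, discharge from the ICU, or unassisted ventilation for 48 hours".
- SAP 9: "No imputation will be applied" to missing data unless the SAP or an amendment says otherwise.
- SAP 11: subjects "will only be included in analyses for which they have available data".
- SAP 12.7.3: scores and changes are summarised as mean and SD, and the score "will be compared between treatment groups using a linear mix-effects regression model".

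Protocol 9.10 requires platelets, creatinine and bilirubin around day 7 in patients still in hospital, whether or not they are in ICU.

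**The concern.** The patients with the worst course leave the comparison, while those who leave ICU stay in it with the best possible value. SOFA at days 3 and 7 serves the secondary objective on systemic organ failure and in-hospital mortality. If one arm has more early deaths, its remaining patients are on average less sick, and its SOFA mean falls for a reason unrelated to better organ function.

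Unequal deaths cannot be ruled out. Protocol 3.6 reports 28-day mortality of 30% on hMSCs and 15% on placebo in phase 2a. The protocol also gives p = 0.24, a baseline APACHE III imbalance and an adjusted hazard ratio of 1.43 (0.40 to 5.12), so this shows only that a difference is possible.

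The zero rule raises a separate question of accuracy. It replaces values that the trial has measured, including those from the part of the discharge day spent in ICU.

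**Working it through.** **1. Does a death before the scoring day have a score?** Carry-forward applies only during the ICU stay, recording ends at death, and there is no default imputation. So a death in ICU before day 3 or day 7 has no value on that day. This follows from silence plus the defaults; no sentence states it. A death on the scoring day itself can still be scored from that day's values. Read literally, a patient who leaves ICU alive and dies on the ward before day 7 scores 0.

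**2. How do other endpoints treat death?**

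| Endpoint | Value for death |
|---|---|
| Ventilator-free days (SAP 8.9) | 0, the worst |
| OSCI (SAP 8.7) | 8, the worst |
| Glasgow score, if missing (SAP 12.7.7) | 3, against 15 for discharge home |
| Non-pulmonary SOFA (SAP 8.3) | none |

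**3. Direction, by arithmetic.** The documents give no SOFA mean, SD or early death rate, so there is no figure of the plan's to reproduce. Assume 60 per arm, 12 discharged (score 0), 39 in ICU at 5, and 9 very sick patients at 12. All 9 die before day 7 in arm A, and 3 of the 9 die in arm B.

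- Survivors only: A = (39 × 5)/51 = 195/51 = 3.82. B = (195 + 6 × 12)/57 = 267/57 = 4.68. A − B = −0.86, favouring A.
- Death scored 5 × 4 = 20: A = (195 + 9 × 20)/60 = 6.25. B = (195 + 72 + 3 × 20)/60 = 5.45. A − B = +0.80.

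With deaths from 6 v 3 to 18 v 9 and a very-sick score of 8 to 16 (15 combinations), the survivors-only difference runs from −0.22 to −2.19 and the death-as-20 difference from +0.20 to +1.80. The extreme end puts phase 2a's 28-day rates (18/60 v 9/60, or 30% v 15%) at day 7, which is unlikely.

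**4. Is the zero rule the cause?** Score the 12 discharged patients 2 instead of 0: A = (24 + 195)/51 = 4.29, B = (24 + 267)/57 = 5.11, A − B = −0.81. The difference hardly moves from −0.86. The missing deaths drive the shift.

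**5. Size in a mixed model.** Simulated trials with 60 per arm, scores on days 0, 3 and 7, no treatment effect on underlying organ function, deaths missing and discharge scored 0. Site, strata and covariates were left out. Day-7 difference, higher-death arm minus lower; negative favours the arm with more deaths:

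| Day-7 deaths and set-up | Raw means | Mixed model | Death = 20 |
|---|---|---|---|
| 15% v 15% | 0.03 | 0.03 | 0.02 |
| 15% v 7.5%, sickest die, 20% discharged | −0.39 | −0.27 | +0.96 |
| 15% v 7.5%, sickest die, 25% discharged | −0.38 | −0.18 | +0.82 |
| 15% v 7.5%, death only more likely as SOFA rises | not reported | −0.11 to −0.13 | not reported |

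For 8% v 4% the mixed-model shift is 0.2 or less, and near zero if death only loosely tracks the score. One estimate varies between trials with an SD of about 0.4 to 0.6. The mixed model uses earlier scores and so reduces the shift. It does not remove it when death follows recent deterioration.

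**6. Zero rule against other rules.** On the day of ICU discharge, the worst-value rule and the zero rule give different scores for the same patient. For a ward patient on day 7, three of the five components (renal, hepatic, coagulation) have required laboratory values, and the zero discards them.

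**The case against.** Early deaths cannot be hidden by a SOFA table. In-hospital mortality is analysed at 14, 28 and 60 days (SAP 12.7.4) and is named in the same objective. OSCI counts death at day 7, ventilator-free days count it over 7 days, and death within 24 hours is a safety endpoint. SAP 12.5 calls the secondary endpoints supportive and exploratory. All of this stands and limits the consequence.

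The size is small against noise. One simulation at 15% v 7.5% gave −0.19 with a standard error of 0.56 and a nominally significant false benefit in about 1% of trials. A reader might infer that a harmful effect would pass as a demonstrated benefit on organ failure; these figures do not support that.

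The reversal of sign is partly mechanical. In step 3, six extra deaths × (20 − 12)/60 = 0.80, the whole of the difference. Organ function in survivors and a score that includes death are different estimands, so the reversal does not show which answer is correct.

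A reader might also blame the zero rule for the tilt, or say that it ignores dialysis. Step 4 answers the first. On the second, SAP 8.3 builds the renal component from creatinine or urine output, so dialysis is not an input. Because recording may stop at ICU discharge, some convention for unmeasured ward components is reasonable.

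Finally, SAP 9 does not forbid a rule for deaths. It allows imputation that the SAP specifies, and none is specified here.

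**Conclusion.** The point holds in a limited form. As written, the plan drops deaths before day 3 or day 7 from the SOFA comparison, out of line with its own handling of death elsewhere. If early deaths differ, the result shifts towards the arm with more of them. For assumed day-7 deaths of 15% v 7.5% (half the phase 2a 28-day rates), the shift is about 0.1 to 0.3 points in a mixed model and 0.3 to 0.5 in raw means, on a 20-point scale. It is 0.2 or less in the mixed model for 8% v 4%. Early death rates, SOFA values and the link between score and death are all assumptions. The direction is steadier than the size.

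Separately, the zero rule contradicts the worst-value rule on the day of ICU discharge and overrides day-7 creatinine, bilirubin and platelets. The primary analysis is unaffected.

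**What to change.** Before unblinding, amend SAP 8.3 and 12.7.3:

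1. Patients who die before day 3 or day 7, including after ICU discharge, take the worst non-pulmonary score of 20 on that day, or rank below every observed score in a rank test. Choose one and name it.
2. Beside it, show the survivors-only result and, per arm and day, the numbers of deaths, ICU discharges and observed scores.
3. Score the day of ICU discharge from that day's worst values.
4. For patients out of ICU but still in hospital, use the components that were measured, and apply 0 only to components that were not.

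The cost is SAP wording and a small change to the derivation program; no new data are needed. The drawback is that the score then combines death with organ failure, which is why the survivors-only table stays.

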8.4 Oxygenation Index

Oxygenation index (OI) will be used as the primary efficacy endpoint. We calculate the oxygenation index with the following validated measure of respiratory function:(5, 15)

$$OI = \frac{FiO_2 (\%) \times \text{mean airway pressure}}{PaO_2}$$

Patient must be ventilated with positive pressure to calculate OI. Otherwise, the mean airway pressure is not reliable.

8.5 Lung Injury Score

Lung Injury Score (LIS) is a validated 4-point score based on chest radiograph findings, PaO₂/FiO₂ ratio, PEEP and compliance.(19) Scoring is performed for each individual component, and the score is the average of the 4 components. Static compliance will be calculated as:

$$\text{Static compliance} = \text{Tidal volume (mL)} / [\text{Plateau pressure (cmH}_2\text{O)} - \text{PEEP (cmH}_2\text{O)}]$$

The scores range from 0 to 4, with higher values representing a worse lung injury. If any of the components are not available, then LIS will be the average of the remaining non-missing assigned scores to the components.

Table 3. Lung Injury Score

	1 points	2 points	3 points	4 points
CXR (# of quadrants with infiltrates)		2 quadrants	3 quadrants	4 quadrants
PaO ₂ /FiO ₂	225-299	175-224	100- 174	< 100
PEEP	6-8	9-11	12-14	≥ 15
Compliance	60-79	40-59	20-39	≤ 19

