7.2 Secondary Endpoints

7.2.1 *Efficacy Secondary Endpoints*

We will test six categories of efficacy endpoints in this Phase 2b trial: respiratory physiology, secondary infection, systemic illness, neurologic, thromboembolic events, and biomarker profiles related to potential mechanism of hMSCs activity in ARDS.

1. **Respiratory Physiology:** Respiratory efficacy endpoints will include:

- Reduction in the 4-point acute lung injury (LIS) score after enrollment in the trial at days 1, 2, 3 and 7, or on the last day of positive pressure ventilation prior to day 7. The LIS is a composite scoring system including the $\text{PaO}_2/\text{FiO}_2$, the level of positive end-expiratory pressure, static respiratory compliance, and the quadrants of frontal chest radiograph with opacification.
- Reduction in the pulmonary dead space on days 1, 2, 3 and 7.
- Reduction in chest radiograph assessment of the extent of pulmonary edema (RALE score) at days 1, 2, 3, and 7.
- OI will be collected (as planned) also on days 2, 3, and 7 if still being ventilated with positive pressure as a secondary endpoint.
- Reduction in ventilatory ratio with measurements at 6, 12, 18, 24, 30, 36 hours, and days 2, 3 and 7.
- Incidence of barotrauma on days 1, 2, 3, and 7.
- Achieving pressure support ventilation with positive end-expiratory pressure equal to or less than 5 cm H_2O for 2 hours.
- Ventilator free-days over 7, 14 and 28 days; duration of assisted ventilation over 28 days in the survivors.

2. **Secondary Infection:** Infection efficacy endpoints will include:

- Superficial incisional/wound infections during the 14 days after enrollment.
- Deep incisional wound infections during the 14 days after enrollment.
- Organ (such as lung, liver) or space (such as peritoneum or pleural) infections during the 14 days after enrollment.
- Ventilator associated pneumonia (VAP) during the 14 days after enrollment.

3. Systemic Illness: Systemic illness efficacy endpoints will include:

- Mean SOFA score (17) at days 3, and 7.
- In hospital mortality at 14 days, 28 days, and 60 days.
- Additional prognostic value of neutrophil to lymphocyte ratio.
- Ordinal Scale for Clinical Improvement (OSCI) at days 7, 14 and 28.

To assess organ failure, we will measure serum creatinine (renal function), bilirubin (hepatic function), and platelet count (hematology) at days 0, 3, 7 and 14.

4. Neurologic: Neurocognitive efficacy endpoints will include:

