12.7 Analyses for Secondary Efficacy Endpoints

12.7.1 Respiratory Physiology Endpoints

The secondary endpoints, such as acute lung injury score, pulmonary dead space and RALE score, expanded oxygenation index up to 7 days and the reduction in ventilator ratios, will be analyzed by linear mix-effects regression models using the modified ITT population, in a fashion parallel to the analyses of the primary endpoint of oxygenation index. Incidence of barotrauma will be analyzed by mixed-effects logistic regression models using the modified ITT population. Counted measures, such as ventilator free days, will be analyzed using zero-inflated negative binomial models in a parallel fashion as well. Achieving pressure support and second infection endpoint will be analyzed using a logistic regression model.

The acute lung injury score (LIS), pulmonary dead space, chest radiograph assessment of pulmonary edema (RALE score) at days 0, 1, 2, 3 and 7 (5 timepoints) will be summarized in modified ITT population by allocated group.

The reduction in ventilatory ratio at 6, 12, 18, 24, 36 hours from the baseline will be summarized in modified ITT population by allocated group.

The incidence of barotrauma will be categorized as yes or not on days 1, 2, 3 and 7, and summarized by patient counts and percentages. Evidence of barotrauma includes the following:

- Pneumothorax
- Bronchopleural fistula
- Tracheobronchial fistula;
- Pneumomediastinum
- Subcutaneous emphysema
- Pneumoatocoele

Ventilator free-days by 7, 14 and 28 days will be calculated as described in *Section 8.7*. They will be summarized as median and interquartile range by allocated group, separately.

Duration of assisted ventilation over 28 days will be calculated among survivors by day 28. It will be summarized as median and interquartile range.

Achieving pressure support ventilation equal to 5 cm H₂O with positive end-expiratory pressure (PEEP) equal to 5 cm H₂O for 2 hours will be categorized as yes or not, and summarized by patient counts and percentages.

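### The lung injury score rule in SAP 8.5 is not tied to the last-ventilated-day clause, so a patient off the ventilator by day 2 or 3 could be scored from the chest film alone

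*SAP*

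**What the plan says.** **Scoring.** SAP 8.5: "Scoring is performed for each individual component, and the score is the average of the 4 components". On direction: "The scores range from 0 to 4, with higher values representing a worse lung injury". On missing components: "If any of the components are not available, then LIS will be the average of the remaining non-missing assigned scores to the components". No minimum number of components is given, and no condition on ventilation status. Protocol Appendix B gives the same scoring table but no missing-component rule.

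**Which day.** SAP 7.2.1 sets the endpoint "at days 1, 2, 3 and 7, or on the last day of positive pressure ventilation prior to day 7". Protocol 6.2.1 and the protocol synopsis carry the same clause.

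**Analysis.** SAP 12.7.1 says that LIS, dead space and the RALE score "at days 0, 1, 2, 3 and 7 (5 timepoints) will be summarized in modified ITT population", and that LIS is modelled in parallel with the oxygenation index (OI). The last-ventilated-day clause does not appear there or in 8.5.

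**Data available after liberation.**
- SAP 6.1.4 records PEEP, tidal volume and plateau pressure only while the patient is on assisted ventilation.
- Protocol 9.9 does not require a day 3 blood gas for study purposes if there is no arterial line. For day 7, Protocol 9.10 says: "Arterial blood gases will be obtained anytime on days 7 if patient still has arterial line".
- The time-events schedule collects chest films when available, with no ventilation condition.
- SAP 6.1.4 stops reference recording at death, ICU discharge or 48 hours of unassisted ventilation.

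**The concern.** Once a patient is off positive pressure, PEEP and compliance no longer exist as components. If there is also no blood gas, the rule in 8.5 leaves the film as the whole score. Enrolled patients have bilateral opacities, so the film usually contributes one of the higher components. A patient who has just been liberated could then record a higher LIS than on the ventilator.

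The two provisions give different values for the same patient, and the SAP does not say which governs at days 2 and 3. Neighbouring measures do have a guard: OI is set to missing on pressure support (SAP 12.6), and dead space is limited to assisted breathing (schedule footnote F). At stake is the interpretability of one secondary endpoint, with an error that would count against an arm that liberated more patients early.

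**Working it through.** **Inputs.** SAP Table 3 assigns 1 to 4 points per component and has no 0-point column. I assume that values milder than the tabulated bands score 0. This reproduces the plan's stated range: minimum (0+0+0+0)/4 = 0, maximum (4+4+4+4)/4 = 4.

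**Step 1. One worked pattern.** Ventilated: 4 quadrants (4), PaO2/FiO2 230 (1), PEEP 5 (0), compliance 45 (2).

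LIS = (4+1+0+2)/4 = 1.75.

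The patient is then liberated and the film improves to 3 quadrants:

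| Treatment of the later visit | LIS | Change from 1.75 |
|---|---|---|
| SAP 8.5, film only | 3/1 = 3.0 | +1.25 |
| SAP 8.5, film plus PaO2/FiO2 of 225-299 (1 point) | (3+1)/2 = 2.0 | +0.25 |
| SAP 8.5, film plus PaO2/FiO2 of 300 or more (0 points) | (3+0)/2 = 1.5 | -0.25 |
| Last-ventilated-day clause applied | 1.75 | 0 |

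The film-only score equals the quadrant count: 2, 3 or 4.

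**Step 2. Is the pattern unusual?** Entry criteria put PaO2/FiO2 below 250 (1 to 4 points); PEEP and compliance can each score 0 to 4. That gives 4 x 5 x 5 = 100 ventilated patterns for each film score.

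| Quadrants, ventilated to film-only | Patterns in which film-only LIS is higher |
|---|---|
| 4 to 4 | 99 of 100 |
| 3 to 3 | 80 of 100 |
| 2 to 2 | 34 of 100 |
| 4 to 3 | 66 of 100 |
| 3 to 2 | 20 of 100 |
| 4 to 2 | 10 of 100 |

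These are counts of score patterns, not patient frequencies. Some patterns fall: components 4/3/3/3 give 13/4 = 3.25 ventilated, and a film-only score of 3 is a drop of 0.25.

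**Step 3. Which visits are exposed?** On its natural reading the endpoint clause covers day 7. Protocol Appendix D allows weaning from 24 hours after enrollment, so liberation before the day 2 or day 3 visit is possible, and those visits can fall inside the 48-hour recording window.

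**Step 4. Treatment contrast.** The bias is the between-arm difference in the proportion of film-only patients times the mean rise. The documents give neither. With an assumed 20% versus 15% and a rise of 1.25: 0.05 x 1.25 = 0.0625, about 0.06 on the 0-4 scale. Equal proportions with the same rise give 0.

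**The case against.** The best defence is that the sections complement each other: 7.2.1 picks the day, and 8.5 deals with a component missing on that day. On that reading a patient liberated between day 3 and day 7 keeps the last ventilated score. The five-day sentence in 12.7.1 is a shared descriptive statement and does not revoke the endpoint definition, and LIS is modelled in parallel with OI, which is missing off positive pressure. This stands for day 7. It does not settle days 2 and 3, because the clause can be read as replacing day 7 only and neither derivation nor analysis section applies it.

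The film-only state is also narrow. Blood gases are scheduled through 36 hours and on day 2; Protocol 9.9 makes the arterial-line exception for day 3 only, although the schedule footnote can be read more broadly. Clinically available PaO2/FiO2 is recorded with the Brussels data to day 14. Patients expected to be extubated within 24 hours are excluded. All of this limits how many patients are affected, but does not remove the case.

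Two stronger readings are tempting. A reader might infer that recovered patients will generally score 3 or 4 at day 7. The documents do not support this: the clause addresses that visit, nothing shows that blood gases are usually absent, and a 3 or 4 needs three or four quadrants still opacified. A reader might also take 20% of an arm times 1.25 = 0.25 as the bias. That is a shift in one arm's mean under an assumed proportion, not a shift in the treatment difference.

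**Conclusion.** The point holds in a limited form. SAP 8.5 permits a film-only LIS, the clause that would prevent it is not carried into 8.5 or 12.7.1, and its reach at days 2 and 3 is ambiguous. For an affected patient the score can rise by as much as 1.25 in the worked pattern; the rise shrinks or reverses once a blood gas is available. The effect on the contrast is probably small (about 0.06 under the assumed 20% versus 15%), and its direction depends on which arm has more such patients.

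This rests on three assumptions: values outside the tabulated bands score 0, the clause is not applied before day 7, and a film is taken without a blood gas. SAP 12.5 treats secondary endpoints as supportive and exploratory, and the primary OI analysis does not use LIS.

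**What to change.** In SAP 8.5 and 12.7.1, before unblinding, state that:
- component averaging applies only to days on positive pressure ventilation;
- at every scheduled visit after liberation (days 2, 3 and 7), the score from the last positive-pressure day is used, as SAP 7.2.1 already provides;
- LIS is never computed from the film alone;
- the number of carried values is reported by arm.

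This costs SAP wording and a change to the derivation code, with no new data. The downside is more carried-forward values, which do not show recovery after liberation.

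The change does not touch a ventilated patient with no film. There 8.5 still averages the other three components, so the pattern above would score (1+0+2)/3 = 1.0 instead of 1.75. The revised 8.5 should say whether that is accepted. A stricter minimum set of components is a matter of preference that the documents do not decide.
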